1. PURPOSE OF PROTOCOL

Specific Aim

To compare Botox-treated and Botox-untreated symptomatic tissues (defined as areas where the head hurts and the pain is felt) of CM patients using targeted transcriptome and genome-wide epigenome analysis. This aim will test the hypothesis that Botox reverses the abnormal expression of inflammatory genes in headache-affected regions and pericranial muscles, fascia, and perineurium of nerves supplying them.

2. SIGNIFICANCE AND BACKGROUND FOR THE STUDY

Background and Rationale

The broad objective of this proposal is to understand better how Botox works and determine whether it can attenuate inflammation. Based on our preliminary findings, we expect the proposed research to vastly expand the understanding of Botox MOA, both in migraine prophylaxis and somatic pain conditions associated with inflammation. Scientifically, we expect to gain new insight into the role played by Botox in environments that surround relevant peripheral nociceptors – potentially by attenuating local expression of pro-inflammatory molecules (mRNA) and their post-transcriptional regulators (non-coding RNA). In the context of migraine, such tissues include the calvarial periosteum, galea aponeurotica, pericranial muscles and fascia surrounding extracranial nerves (e.g., occipital, supraorbital, auriculotemporal nerves). In the context of other somatic pains, such tissues include muscles, fascia, and the perineurium. The potential impacts of the proposed research is that if successful, it will broaden the clinical use of Botox. Equally important, it will define a novel framework for conceptualizing about Botox MOA and consequently, why and how it may be used to treat other pains and possibly conditions associated with abnormal inflammatory and immune responses.

The goals of the proposed research will be achieved by studying tissues commonly discarded during nerve decompression surgeries performed to alleviate neck and head pain in chronic migraineurs. These goals were formulated on the basis of two sets of preliminary clinical findings. The first showed that gene transcripts (mRNA) that promote immune and inflammatory responses are significantly upregulated in calvarial periosteum of CM patients (as compared to control subjects) and that gene transcripts (mRNA) that reduce immune and inflammatory responses are significantly down-regulated in calvarial periosteum of CM patients (as compared to control subjects).

In more detail, there is new evidence of extracranial origins of migraine headache. Clinically, there is data that describes an imploding headache (extracranial) versus exploding headache (intracranial) [1]. There is evidence that expression of proinflammatory genes (eg, CCL8, TLR2) in the calvarial periosteum is significantly increased in CM patients, whereas expression of genes that suppress inflammation and immune cell differentiation (eg, IL10RA, CSF1R) is decreased. It is well known that anti- inflammatory drugs improve migraine attacks. It has further been shown that extracranial administration of OnabotulinumtoxinA is effective in reducing the number of migraine days per month in patients who testified to having 'imploding', but not in those who testified to having 'exploding' headache [2]. The identification of extracranial pathophysiologies in chronic migraine patients whose headaches are most commonly perceived as imploding, and the finding that imploding migraine patients are those who benefit most from prophylactic treatment with OnabotulinumtoxinA [1], gave rise to a theory that Botox may help patients with imploding headache due to anti-inflammatory properties.

3. DESCRIPTION OF RESEARCH PROTOCOL

A. Study Design – Overview, Methods, Procedures

Overall study design:

Patients diagnosed with chronic migraine (fulfill criteria for CM as defined in the ICHD-3 beta), especially those complaining about chronic muscle tenderness, are routinely considered good candidate to benefit from a surgery in which trapped nerves are decompressed. In routine clinical care, such patients are referred to [name] (plastic surgeon performing these procedures) to determine whether or not they fit to undergo the nerve decompression procedure. Of great importance to the evaluation of the proposed study is the fact that the decision on whether or not to operate is unrelated to and independent of any academic study. Those deemed good candidate for the surgery, which include fulfilling all inclusion/exclusion criteria, would be presented with an option to hear about the study from a research nurse. Those interested in hearing about the study will be presented with all the necessary details required and then given the option to sign (or not to sign). They will be given as much time as needed to sign the consent form and have the option to take the consent form home and call in interested.

Since the surgery itself is unrelated to the proposed study, all patients (those who sign the informed consent and those who chose not take part in the study) are booked for the surgery. Usual waiting time is 3-6 month.

Those who agree to participate in the study, will be asked to fill out a 15min headache questionnaire that contains questions about their headaches. Subjects will also be asked to complete a headache diary 3 months prior to botox injections.

Enrolled subjects will be booked for another visit to [name] clinic 30 days prior to their planned surgery. In this visit, they will be injected with 40 units of Botox in one side of their head/neck as detailed below.

During surgery, calvarial periosteum, pericranial muscles and fascia surrounding nerves that are routinely removed and discarded, will be collected by [name], stored in in RNAlater Solution, Ambion, CA, de-identified, frozen, and shipped overnight to [name] lab at BIDMC, where each sample will be recorded, verified, prepared for processing, and analyzed for targeted transcriptome and epigenome involved in inflammatory and immune responses.

Clinical Site Study Procedures

The following research study activities will take place exclusively at MGH:

Those who agree to participate in the study, will be asked to fill out a 15min headache questionnaire that contains questions about their headaches. Subjects will also be asked to complete a headache diary 3 months prior to botox injections.

The headache diary will be filled out every day for 3 months prospectively prior to botox injection. Subjects will indicate whether they had migraines that day (check date box), what severity the migraines were (on a scale of 0-10), what the duration was (hours), what the location was, which other symptoms they experienced, which medications they took, how often they went to the ED, saw doctors or missed work and how much the total cost was. The total time spent every day filling out the diary should not exceed 5min.

Enrolled subjects will be injected with Botox on one side of the back of the head. The FDA-approved injection paradigm includes 7 muscles (Frontalis, Corrugator, Procerus, Occipitalis, temporalis, Trapezius, and the Cervical Paraspinal muscle group), 31 sites and 155 units divided as follows: Frontalis – 4 sites, 5 units in each; Corrugator – 2 sites, 5 units in each; Procerus – 1 site, 5 units; Occipitalis – 6 sites, 5 units at each; Temporalis – 8 sites, 5 units in each; Trapezius – 6 sites, 5 units at each; Cervical

Paraspinal – 4 sites, 5 units in each.

Of these muscles, sites and doses, patients will be injected (from a 100 Unit vial of OnabotulinumtoxinA reconstituted per product manufacturer label instructions) as follows:

- (A) 2 sites in the Occipitalis muscle (5 units each)
- (B) 4 sites in the Cervical Paraspinal muscle group (5 units each)
- (C) 2 sites in the Trapezius muscle (5 units each)

These injections will be given into one side only. This deviates from the standard of care, as Botox is usually injected on both sides if pain is experienced on both sides. The selection will be random based on subject number. Odd numbers will be injected on the right and even numbers on the left.

The current standard of care for screening for migraine surgery includes injection of Botox to identify nerve triggers. In the occipital region, botox is either injected unilaterally or bilaterally depending on where pain occurs. When pain occurs bilaterally, Botox is injected on both sides. Subjects included in this study have bilateral occipital pain and would therefore as part of routine standard care be injected on both sides. As per this protocol, subjects will only be injected on one side. The risks of unilateral injection of botox (in addition to the risk of Botox in general outlined by the FDA) include continued pain on the uninjected side and/or injected side and one- sided muscle weakness, one- sided bruising, one sided infection on the injected side. More generally, botox injections may cause the formation of anti-botox antibodies, which may decrease the effectiveness of botox treatment in other areas.

Subjects will be informed that they have the option to be injected with Botox on the uninjected side if any unwanted symptoms are experienced on the uninjected side. The cost of injection on the other side will be covered by the study funds.

Because the standard surgical procedure involves removal of equal amount of corresponding tissues from both sides of the head, an opportunity is created here to analyze identical Botox-treated and Botox-untreated tissues. Importantly, all analyzed tissues are discarded as a part of the surgery and none is collected for the sake of the study.

Note that this injection paradigm does not deviate from the currently approved FDA paradigm and that it is given to chronic migraine patients (i.e., for the indication it was approved by the FDA). Also note that one of the standard clinical criteria that these patients must fulfill in order to qualify for the surgical decompression procedure (which is unrelated to the study) is to demonstrate that they have failed at least 3 attempts to treat their chronic migraine with prophylactics – one of which is Botox. Thus, all those who qualify for the study would have been treated with Botox at least twice before as per the FDA approved protocol.

Thirty days later, patients will undergo a study-unrelated nerve decompression surgery. This procedure involves the removal of different tissues surrounding trapped branches of the occipital nerve. These tissues include muscles, fascia, and periosteum (discarded tissue). The amount of tissue removed at each area is many folds larger than the amount of tissue needed for sampling (less than the size of 1 grain of rice).

From the time of informed consent and for 3 months following injection, all self-reported adverse events will be reviewed by the study physician at each patient contact (patients are followed every 4 weeks after botox injection and one week, one month, three months, one year and after that yearly after surgery). All serious adverse events will be reported to the IRB and designated safety monitor within 24 hours of awareness of the event.

There will be two visits:

Screening visit: Patients will be screened for eligibility. This will be performed during the regular clinical assessment for surgery. The study visit will take 30min. The subject will be asked to complete

a 15 min questionnaire and will be asked to fill out a 3m headache diary which may take up to 5min a day.

Preoperative visit: will be injected with Botulinum Toxin. This will take 30 minutes.

There will be further routine clinical visits postoperatively (one week, 3 months and 12 months). However, these visits are not related to the study but are part of regular follow up. No study materials for this study will be collected as part of this visit.

[figure not shown]
Analysis to be Done at BIDMC

- (A) Tissue processing, RNA isolation, genetic processing and mRNA counting will occur in [name] lab at Beth Israel Deaconess Medical Center, Harvard Medical School.
- (B) Bioinformatics and biostatistics analyses will be conducted at [name] lab at Beth Israel Deaconess Medical Center, Harvard Medical School.

B. Statistical Considerations

Statistical power analysis: In doing the power calculation, we control for false discovery rate (FDR), a common method used in genome level analysis to control for multiple testing of a large number of genes. The statistical power is also a function of proportion of non-differentially expressed genes using the method developed by Liu and Hwang in 2007. Based on our feasibility study findings, we used 98% non-differentially genes and effect size of 1.5 for power calculation. With 50 chronic migraine (each serving as his/her own control), we will have 95% statistical power to detect effect size of 1.5, with stringent FDR of 0.001.

Figure 2. Power vs. Sample Size with $fdr=0.001$ and $\Delta/\sigma=1.5038$

Statistical analysis for main outcome measure: (A) Comparisons of targeted transcriptome from periosteal, muscles and fascia surrounding nerves will be performed between corresponding injected and not-injected tissues using Wilcoxon's Matched Pairs Tests.

Quality controls (QC), normalization and preprocessing analysis of genomics profiling data : Tissues genomics profiling data will be analyzed using the following major steps:

- (a) Quality control: We will first assign a quality measure for each sample based on nanostring standard QC criteria such as FOV counted, binding density, array mean signal, average background, and scaling factor using expert bioinformatician supervision. We will also check for reproducibility of the samples using correlation and signal-to-noise ratio (SNR) methods for replicate arrays. Low quality arrays will be excluded from further analysis.
- (b) Normalization: Normalization is the most critical step in the analysis, which is a transformation of signal values so that different chip results become comparable. The normalization will be performed in three steps: (i) Positive Spike in controls based normalization that will take care of signal variation due to different amounts of input RNA, (ii) Negative Spike in controls based background correction, (iii) Normalization based on signal values of house keeping genes from the experiments to bring all

the chips onto a similar expression level. The different normalizations and QC's will be performed using the Bioconductor R packages workflows.

(c) Unsupervised analysis: To identify unbiased patterns of similarity, outlier arrays and batch effects, unsupervised learning technique will be performed on the normalized expression profiles of all genes. The unsupervised learning will be carried out using the Unweighted Pair Group Method with Arithmetic Mean (UPGMA), also referred to as hierarchical clustering. The assumption underlying these clustering techniques is that expression profiles that are proximate in Euclidean or correlation space are mechanistically related. Additionally attempt to identify outliers will be done using principal component analysis.

Identification of Botox signatures: In this analysis, we will consider the gene expression as the dependent variable and the indicator variable of group (e.g. Botox vs. No Botox) as the independent variable. The analysis will be performed using Linear Models for Microarray Data (LIMMA) as it employs an empirical Bayes approach for parameter estimation. To reduce the false positive, the significantly differentially expressed genes will be obtained using Benjamini and Hochberg multiple test corrected P value. The genes with P value < 0.01 and absolute fold change of at least 2 folds will be considered as differentially expressed. Due to differences in level of expression of gene in different tissues, we will perform separate normalization and signature identification for each tissue type.

Functional and Pathways analysis: The genes from different tissues will be further analyzed in the context of biological pathways, Gene Ontology (GO) and functional categories. The analysis will be performed using MATLAB, Bioconductor and commercial packages (e.g. Ingenuity pathways Analysis). Identifying significantly over-represented biological pathways is particularly valuable for understanding the underline mechanism of action of Botox.

Identification of tissues and pathways that potentially drive Botox effects: The comprehensive network generated above will be further analyzed to pin-down the involved tissues and pathways. To reach this goal, an effort will be made to find a sub-network with highest number of alterations. Such subnetwork will be identified using HotNet package that considers gene as a unit heat source, and uses a diffusion process to derive "hot" subnetworks that contain more alterations than expected by random chance. *In principle, significant subnetworks are routinely determined by both the frequency of alteration of genes and the local topology of the subnetwork.* To identify a key pathway(s) in a top significant subnetwork, we will use the Biological pathway enrichment analysis. This analysis will be done using various modules of Bioconductor, which uses multiple corrected hypergeometric tests to determine significance of pathway or biological process affected.

C. Subject Selection

Patients diagnosed with chronic migraine (fulfill criteria for CM as defined in the ICHD-3 beta), especially those complaining about chronic muscle tenderness, are routinely considered good candidate to benefit from a surgery in which trapped nerves are decompressed. In routine clinical care, such patients are referred to [name] to determine whether or not they fit to undergo the nerve decompression procedure. Of great importance to the evaluation of the proposed study is the fact that the decision on whether or not to operate is unrelated to and independent of any academic study. Those deemed good candidate for the surgery would be presented with an option to hear about the study from [name], the plastic surgeon responsible for their well-being during the surgery and the one handling the discarded tissues. Those interested in hearing about the study will be presented with all the necessary details required by the Western IRB and then given the option to sign (or not to sign).

Accordingly, up to ~~50~~ 65 chronic migraine patients will be recruited to the study (if they are found fit to undergo the surgery) by [name], a certified plastic surgeon with enormous experience in performing these procedures.

Inclusion Criteria:

- Age 18-65 years
- Diagnosis of Chronic Migraine consistent with International Classification of Headache Disorders (ICHD-III) criteria, with a history of bilateral headache pain and chronic tenderness in neck muscles
- Patient is capable and willing to provide informed consent
- Female subjects of child bearing potential must have a negative pregnancy test at enrollment and agree to remain abstinent or use acceptable methods of birth control (i.e., hormonal contraceptives, intrauterine device, diaphragm with spermicide, cervical cap or sponge, condoms or partner has had a vasectomy) for three months following injections of Botox
- Patients referred by their primary Neurologist to the study surgeon and who are determined to be candidates for surgical decompression of extracranial sensory nerves.
- Patient agrees to abstain from protocol-specific excluded medications (see Appendix A) beginning 14 days prior to the decompression surgery.

Exclusion Criteria:

- Patient has hypersensitivity reactions or other intolerance to Botox
- Patient is pregnant or trying to become pregnant with the timeframe of the study.
- Infection at proposed injection sites

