8. DATA SECURITY

All clinical study records will be stored in a secure location in the office of [name], as all research activities involving patient data will take place at MGH.

De-identified discarded tissue will be transferred to [name] lab at Beth Israel Deaconess Medical Center for processing and analysis. No personally identifiable data (including name, date of birth, age, and gender) will be shared between the clinical site (Boston) and the processing site (BIDMC).

[figure not shown]
9. Dissemination of Research Results

[name] will provide participants with the option to learn about findings generated as a result of their participation. A copy of the final published manuscript will be provided to subjects who express interest in receiving a copy of the primary manuscript.

10. Botox administration

Botox Prior to Surgery

As stated above, patients diagnosed with CM affecting both sides of the head who have been deemed candidates for *study-unrelated* surgical decompression of extracranial sensory nerves will be presented with an option to hear about the study and sign the informed consent. Those who agree to participate in the study will be injected with Botox (Fig. 1) on one side of the neck/back of the head per FDA approved guidelines for migraine prophylaxis. Botox treatment will take place 30 days prior to surgery. As before, during surgery, perineurium, fascia, muscle, and periosteum will be collected (in RNAlater Solution, Ambion, CA), de identified, frozen, and shipped overnight for processing and analysis for targeted transcriptome and epigenome involved in inflammatory and immune responses using the advanced nanostring system.

Injection paradigm:

Occipital - 1 injection of 10 units
Trapezius - 2 injections of 10 units each
Semispinalis - 1 injection of 10 units
Splenius Capitis - 1 injection of 10 units

Headache Diary

Month/Year: _____

Participant ID# _____

Date	Maximum Severity (0-10)	Duration (hours)	Location	Nauseau Y N	Vomiting Y N	Sensitive to Light Y N	Throbbing Y N	Muscle Pain Before HA Y N	Muscle Pain During HA Y N	Muscle Pain After HA Y N	Acute HA Medicine (name/s)	No. of Doses	Number of ER & Doctor Visits, Work Days Missed	Total Cost (medications, doctor & ER visits, work days missed)
□ 1				□ □	□ □	□ □	□ □	□ □	□ □	□ □				
□ 2				□ □	□ □	□ □	□ □	□ □	□ □	□ □				
□ 3				□ □	□ □	□ □	□ □	□ □	□ □	□ □				
□ 4				□ □	□ □	□ □	□ □	□ □	□ □	□ □				
□ 5				□ □	□ □	□ □	□ □	□ □	□ □	□ □				
□ 6				□ □	□ □	□ □	□ □	□ □	□ □	□ □				

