2.4 Chronic Migraine

The recommended dilution is 200 Units/4 mL or 100 Units/2 mL, with a final concentration of 5 Units per 0.1 mL (see Table 1). The recommended dose for treating chronic migraine is 155 Units administered intramuscularly using a sterile 30-gauge, 0.5 inch needle as 0.1 mL (5 Units) injections per each site. Injections should be divided across 7 specific head/neck muscle areas as specified in the diagrams and Table 2 below. A one inch needle may be needed in the neck region for patients with thick neck muscles. With the exception of the procerus muscle, which should be injected at one site (midline), all muscles should be injected bilaterally with half the number of injection sites administered to the left, and half to the right side of the head and neck. The recommended re-treatment schedule is every 12 weeks.

Diagrams 1-4: Recommended Injection Sites (A through G) for Chronic Migraine

[figure not shown]

Table 2: BOTOX Dosing by Muscle for Chronic Migraine

Head/Neck Area	Recommended Dose (Number of Sites ^a)
Frontalis ^b	20 Units divided in 4 sites
Corrugator ^b	10 Units divided in 2 sites
Procerus	5 Units in 1 site
Occipitalis ^b	30 Units divided in 6 sites
Temporalis ^b	40 Units divided in 8 sites
Trapezius ^b	30 Units divided in 6 sites
Cervical Paraspinal Muscle Group ^b	20 Units divided in 4 sites
Total Dose:	155 Units divided in 31 sites

^a Each IM injection site = 0.1 mL = 5 Units BOTOX

^b Dose distributed bilaterally

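### The protocol gives two different Botox regimens for the same pre-surgery treatment (40 units in 8 sites, 50 units in 5 injections), and neither matches the label it claims to follow

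*Combined protocol and SAP*

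**What the plan says.** **Section 3.A.** The overall design states a total: "they will be injected with 40 units of Botox in one side of their head/neck as detailed below". Clinical Site Study Procedures gives the breakdown:

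- "2 sites in the Occipitalis muscle (5 units each")
- "4 sites in the Cervical Paraspinal muscle group (5 units each")
- "2 sites in the Trapezius muscle (5 units each")

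The Partners Human Research Committee Protocol Summary repeats both the 40-unit total and this breakdown.

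**Section 10, Botox administration.** This section refers back to the earlier text and covers the same one-sided injection 30 days before surgery. Its list includes "Trapezius - 2 injections of 10 units each", plus one 10-unit injection each for the occipital, semispinalis and splenius capitis entries. It prints no total.

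**Conformity with the label.** After its list, Section 3.A says: "Note that this injection paradigm does not deviate from the currently approved FDA paradigm". Shortly before, it says: "These injections will be given into one side only. This deviates from the standard of care". Section 10 also describes its injection as given under FDA-approved guidance for migraine prophylaxis. The appended prescribing information (2.4 Chronic Migraine) sets 5 units at each site and, apart from the midline procerus, says "all muscles should be injected bilaterally with half the number of injection sites administered to the left" and half to the right.

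**The concern.** Both lists stand in current text, both are complete and legible, and both describe the same treatment. A person giving the injection, or an ethics committee approving it, cannot tell from the protocol which one applies.

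For the analysis, the only comparison is injected against uninjected tissue within a subject. Section 3.B models it with a two-level indicator (Botox or no Botox) and has no term for dose. Any difference in dose or muscle lies on the treated side alone, so pairing does not remove it; it goes straight into the within-subject difference. Each sample is smaller than a grain of rice and comes from muscle, fascia or periosteum, so local exposure can depend on which muscle received how much. If both lists were used, the treatment effect would vary between subjects for a reason that the planned analysis neither records nor models.

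The claim of label conformity supports the protocol's account of risk. Section 5 reasons from where the injections are given when it calls some adverse effects very unlikely. That reasoning needs a fixed injection scheme behind it.

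**Working it through.** Each total is the sum over muscles of (sites × units per site).

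**1. The stated 40 units (Section 3.A).** (2 + 4 + 2) sites × 5 units = 8 × 5 = 40 units. The stated total is reproduced.

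**2. The Section 10 list.** (1 + 2 + 1 + 1) injections × 10 units = 5 × 10 = 50 units. This does not reproduce 40. The excess is 10 units, and 50/40 − 1 = 25%.

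**3. The label (2.4, Table 2).** 4 + 2 + 1 + 6 + 8 + 6 + 4 = 31 sites, and 31 × 5 = 155 units, which agrees with the label's own total. Half the sites of each relevant area fall on one side:

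- occipitalis 6/2 = 3 sites, 15 units
- trapezius 6/2 = 3 sites, 15 units
- cervical paraspinal 4/2 = 2 sites, 10 units
- sum: 8 sites, 40 units

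**4. Side by side, injected side only.**

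| | Section 3.A | Section 10 | Label, one side |
|---|---|---|---|
| Units per injection | 5 | 10 | 5 |
| Number of injections | 8 | 5 | 8 |
| Occipital | 10 units (2 sites) | 10 units (1) | 15 units (3) |
| Trapezius | 10 units (2) | 20 units (2) | 15 units (3) |
| Cervical paraspinal | 20 units (4) | not named | 10 units (2) |
| Semispinalis and splenius capitis | not named | 20 units (2) | not named |
| Total | 40 | 50 | 40 |
| Sides treated | one | one | both |

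**5. Can the two lists be read as one?** The documents do not say whether semispinalis and splenius capitis belong to the cervical paraspinal group. Assume that they do. The paraspinal dose is then 20 units in both lists, and the occipital dose is 10 in both. What still differs is the trapezius dose (10 against 20 units), the units per injection (5 against 10), the number of injections (8 against 5) and the total (40 against 50). The lists conflict under either reading.

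**6. Does either list follow the label?** The Section 3.A list has the label's 5 units per site and its one-sided total of 40. Its split over occipitalis, trapezius and paraspinal is 2/2/4 sites where the label has 3/3/2, so the number of paraspinal sites that the label spreads over two sides is placed on one. It is also one-sided and leaves out the other muscle areas. The Section 10 list differs in laterality and distribution as well, and further in units per site and in the one-sided total.

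**The case against.** Four points can be made for the plan.

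- **The 40-unit list is the consistent one.** Its total and breakdown each appear in Section 3.A and again in the Protocol Summary, and they agree. Section 10 stands alone, and it points to a figure that is not available here. This shows where the discrepancy sits. It does not remove it: Section 10 is the section headed for administration, and it is current text.
- **The label conflict is milder for the 40-unit list.** Its total, number of sites and units per site equal the label's one-sided amounts. Section 3.A also discloses that one-sided injection departs from usual care, and the parallel paragraph of the Protocol Summary omits the no-deviation sentence. All of this is true. The split by muscle, the one-sided delivery and the omitted areas still contradict a statement of no deviation.
- **Heterogeneity is conditional.** Injections are given at one clinic, and nothing says that both lists would be used. The occipital dose is the same in both, and the tissue removed surrounds branches of the occipital nerve. Mixed dosing would vary the effect between subjects but would not by itself bias the injected-against-uninjected comparison. This stands. Even with a single regimen in practice, though, the protocol would not say which exposure the results describe.
- **The risk section is mostly general product risk** and does not depend on 40 or 50 units. This is largely right. Only its argument from the injection location is tied to the scheme.

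**Conclusion.** The concern holds. The current text contains two incompatible regimens for one treatment: 8 sites and 40 units, or 5 injections and 50 units. They differ by 25% in total dose, and two-fold in units per injection and in trapezius dose. The 50-unit figure is a sum that the protocol does not print. The conflict does not depend on how semispinalis and splenius capitis are classified.

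The statements of label conformity in Sections 3.A and 10 disagree with the appended label, more so for the Section 10 list than for the Section 3.A list.

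The effect on the analysis cannot be sized from the documents. The power statement in Section 3.B makes no use of dose, and between-subject variation in exposure arises only if both lists are used. The point is still a must-fix: it concerns what is injected into patients, it bears on the trial's only contrast, and it is cheap to correct.

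**What to change.** 1. Reconcile Section 3.A (the overall design and Clinical Site Study Procedures), Section 10 and the matching parts of the Protocol Summary to one injection table giving muscle, number of sites, units per site and total. The investigators decide its content; none is proposed here. Every other place should refer to that table and not restate it.
2. Reword the conformity statements in Sections 3.A and 10 so that they agree with the table and with section 2.4 of the appended label, and say plainly where the study departs from it. Then check that the location-based reasoning in Section 5 still fits.
3. Record for each subject the side, the muscles and the units actually given per muscle, so that exposure can be checked when the tissue results are analysed. If injections have already been given, document which list was followed for each subject.

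The cost is a protocol amendment and a few fields on the injection record. No visit, procedure or sample is added.
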